## 6.4 Safety and Other Assessments

The following safety assessments will be performed by appropriately trained staff/clinical examiners, at the times and in the order defined in the Schedule of Activities of this protocol.

### 6.4.1 Oral Soft Tissue (OST) Examination

This procedure will be conducted by a qualified, experienced clinical examiner. The OST examination will be accomplished by direct observation and palpation with retraction aids, as appropriate. The examination will cover the oral labial mucosa (including lips), buccal mucosa, mucogingival folds, gingival mucosa, hard palate, soft palate, tonsillar area, pharyngeal area, tongue, sublingual area, submandibular area and salivary glands. Findings from the examination will be recorded in the CRF as either normal or abnormal, with details of any abnormalities. The results of the OST examination performed at screening will be used to determine subject eligibility. Any new OST abnormality or worsening of a pre-existing condition observed by the clinical examiner or reported by the subject after the screening examination will be recorded as an AE.

Where possible, this procedure should be conducted by a single clinical examiner.

### 6.4.2 Oral Hard Tissue (OHT) Examination

This procedure should be conducted by a qualified, experienced clinical examiner. The OHT examination will be accomplished by direct observation, using retraction aids as appropriate and will identify any grossly carious lesions, signs of erosive wear, enamel irregularities, tooth fracture, gross generalized dental caries decay, decalcification and faulty restorations. The presence of any implants, fixed or removable dentures, fixed or removable orthodontic braces/bands, fixed orthodontic retainers, full crowns or veneers will be recorded. Observations will be listed as either absent or present, and conditions noted as present will be described in the CRF. Any change observed by the clinical examiner or reported by the subject after the screening examination will be recorded as an AE.

The results of the OHT examination performed at Screening will be used to determine subject eligibility.

Where possible, this procedure should be conducted by a single clinical examiner.

## 7 INVESTIGATIONAL/STUDY PRODUCTS

For the purposes of this study, per International Conference on Harmonization (ICH) guidelines, and Haleon policy, study intervention is defined as any investigational intervention(s), marketed product(s), placebo, or medical device(s) intended to be administered to a study participant according to the study protocol.

Property of Haleon- Confidential

May not be used, divulged, published or otherwise disclosed without the consent of Haleon

This includes a product with a marketing authorization when used or assembled (formulated or packaged) in a way different from the approved form, or when used for an unapproved indication, or when used to gain further information about an approved use.

## 7.1 Investigational/Study Product Supplies

The following study products will be supplied by the Clinical Supplies Department, Haleon:

**Table 7-1** **Investigational/Study Product Supplies**

	Test Dentifrice	Positive Control Dentifrice	Reference Dentifrice
Product Description	Dentifrice containing 5% w/w NovaMin and 1040ppm fluoride as sodium fluoride	Dentifrice containing 5% w/w KNO 3 and 1150ppm fluoride as sodium fluoride	Dentifrice containing 1100ppm fluoride as sodium fluoride
Product Name	Sensodyne Repair and Protect Original Mint	Sensodyne Fresh Mint	Crest Cavity Protection Regular
Product Master Formulation Code	Commercial product – Canada marketplace CCI	Commercial product – Canada marketplace CCI	Commercial product – Canada marketplace
Pack Design	Carton of overwrapped tubes		
Dispensing Details	Dentifrice kit dispensed at Screening Visit		
Return Requirements	All used/unused samples to be returned		
Dose/Application	Subjects will dose the toothbrush provided with a strip of dentifrice (a full brush head) on each brushing occasion. Subjects will brush for one timed minute twice daily (morning and evening); subjects will be permitted to rinse with water post-brushing.		
Route of Administration	Oral topical		

**Table 7-2** **Sundry Items**

Sundry Items to be supplied:

Item	Supplied By	Pack Design	Dispensing Details	Return/Disposal Details	
				Used Samples	Unused Samples
Sensodyne Sensitive Care soft bristle toothbrushes [Canada Marketplace]	Haleon	Twin Pack	One pack at Screening (Visit 1)	Destroy at site using site disposal procedures	Return

Property of Haleon- Confidential

May not be used, divulged, published or otherwise disclosed without the consent of Haleon

Countdown Timer	Haleon	Individual commercial pack	At Screening (Visit 1)	To be kept by subject or disposed of.	Return
Opalescence Go 15% Peroxide Kit [Canada Marketplace]	Study Site	Commercial pack	First use at site, dispensed for at-home use at Visit 2	Destroy at site using site disposal procedures	Destroy at site using site disposal procedures
Petroleum Jelly	Haleon	Commercial pack	First use at site, dispensed for at-home use at Visit 2	Destroy at site using site disposal procedures	Return

The toothbrush is a marketed medical device and will be used in accordance with the label instructions.

### 7.1.1 Application of the Peroxide Bleaching

The peroxide bleaching should be performed at-home (except for the first application which will be performed under supervision at the study site). Subjects should apply their peroxide-containing trays to their teeth (both maxillary and mandibular) once per day for 15 timed minutes in accordance with the manufacturer's instructions. Subjects should then brush their teeth in accordance with the tooth brushing instructions. Subjects should attempt to perform the tooth bleaching at the same time of day wherever possible. Subjects should perform peroxide bleaching for 7 consecutive days. Should subjects experience gum sensitivity/irritation due to the peroxide, they should apply a thin layer of the supplied petroleum jelly to the affected gum tissue prior to applying the peroxide, taking care not to contact the teeth with the petroleum jelly.

## 7.2 Product Supplies Product Storage, Accountability, Returns and Destruction

All study products supplied are for use only in this clinical study and should not be used for any other purpose.

Guidance will be provided to the Investigator and site staff for the receipt, storage and management of products for the duration of the trial by Haleon Clinical Supplies during the Site Initiation Visit and with further instructions included with the shipping documentation.

The site should ensure that the room or area set aside for storage is able to maintain the correct temperature to meet the product label storage conditions, is sufficient to store all products and is secure and access controlled.

Any temperature excursions or discrepancies during transit or whilst study products are stored at site require the affected products to be quarantined and this must be communicated immediately to the Sponsor who will provide documentation to approve further usage.

Use of any of the affected product(s) prior to sponsor approval will be considered a protocol deviation.

Study products are to be dispensed only to subjects enrolled in the study in accordance with the protocol, by authorized site staff. Subjects will be informed on product usage, storage, return and what to do in the event of product loss when they are first dispensed after enrolment.

All study products will be accounted for using the investigational/study product accountability form/record. The Investigator is responsible for study product accountability, reconciliation, and record maintenance.

Detailed instructions for the return of study product/study supplies will be provided by Haleon during the study in time for study close out. Investigational products can only be destroyed at site in agreement with and after approval from the Sponsor.

### **7.3 Blinding and Randomization**

Subjects will be randomized into the study provided they have satisfied all subject selection criteria.

Subjects will be randomized to one of the study products with a 1:1:1 allocation ratio using an Interactive Response Technology (IRT). The randomization schedule will use a stratified randomly permuted block design. Stratification will be based on the clinically diagnosis of DH at -Screening (Yes/No). Approximately 45% (40-50%) of randomized subjects should have clinically-confirmed DH.

Study products will be provided to subjects in individual packs (cartons); each carton will contain overwrapped tubes of study product. The carton and tubes of study product will be labelled with the same unique container number. Subjects will be assigned to container numbers associated with cartons containing only their randomized study product using an Interactive Response Technology (IRT); product codes will not be used.

Returned study products should not be re-dispensed to any subject.

This study is described as examiner-blind (the clinical examiner will be blinded to the product received).

To ensure the examiner remains blinded throughout the study, staff involved in the preparation and dispensing of study products will work in a separate area.

Subjects will be instructed not to remove study products from the opaque bags provided/cartons outside of the dispensing room, while at the study site. Dispensing staff will not be involved in any efficacy/safety assessment procedures during the study.

Site staff, study statistician(s), data management staff and other employees of the sponsor and vendors acting on behalf of the sponsor, who may influence study outcomes will be blinded to the product allocation.

### **7.4 Breaking the Blind**

At the initiation of the study, the study site will be instructed on the method for breaking the blind. The method will be an electronic process.

The electronic system will be programmed with blind-breaking instructions. In case of an emergency, the investigator has the sole responsibility for determining if unblinding of a subject's product assignment is warranted. Subject safety must always be the first consideration in making such a determination. If the investigator decides that unblinding is warranted, the investigator should make every effort to contact the sponsor prior to unblinding a subject's product assignment unless this could delay emergency treatment of the subject.

If a subject's product assignment is unblinded, the sponsor must be notified within 24 hours after breaking the blind. The date and reason that the blind was broken must be recorded in the source documentation and case report form, as applicable.

Property of Haleon- Confidential

May not be used, divulged, published or otherwise disclosed without the consent of Haleon

## 8 STATISTICAL CONSIDERATIONS AND DATA ANALYSES

### 8.1 Sample Size Determination

No formal sample size calculation was performed for this study. The sample size requirement of approximately 30 randomized subjects per arm is based on feasibility due to the exploratory (proof-of-principal) nature of the study, whilst ensuring an adequate number of subjects to address the study objectives ([Kieser and Wassmer, 1996](#)).

### 8.2 Populations for Analysis

- The Safety population will comprise all randomized subjects who receive at least one dose of the study product. This population will be based on the product the subject actually received.
- The modified Intent-To-Treat (mITT) population will include all randomized subjects who complete at least one use of study product and have at least one VAS score for tooth sensitivity recorded during the tooth-bleaching period. This population will be based on the study product to which the subject was randomized. Any subject who receives a randomization number will be considered to have been randomized.
- The Per-Protocol (PP) population will include all randomized subjects who do not have any protocol deviations that could confound the interpretation of analyses conducted on the mITT.

#### 8.2.1 Exclusions of Data from Analysis

Exclusion of any data from the analyses will be agreed during a Blinded Data Review (BDR) Meeting prior to database lock. Any reasons for exclusion of a subject from an analysis population or data from an analysis will be listed, if applicable.

### 8.3 Statistical Analyses

This section describes the planned statistical analyses of the study endpoints. Any amendments or clarifications to the details here will be documented in the blinded data review documentation prior to database lock and unblinding.

Categorical variables will be summarized by the number and percentage of subjects with each relevant characteristic in each study product group. Continuous variables will be summarized by mean, standard deviation (SD), standard error (SE), median, minimum and maximum values in each study product group. The number of missing and non-missing data will also be presented.

#### 8.3.1 Primary Endpoint Analysis

The modified Intent-to-Treat (mITT) population will be used for the primary analyses.

The primary endpoints are:

- Daily VAS scores collected through the study
- Daily LMS scores collected through the study
- Daily Bothersomeness scores collected through the study
- Daily number and % of subjects with a tooth sensitivity-free day through the study
- Daily number and % of subjects with analgesic used to alleviate tooth sensitivity through the study

Property of Haleon- Confidential

May not be used, divulged, published or otherwise disclosed without the consent of Haleon

Each endpoint will be summarized descriptively at Screening and Visit 2 (pre-bleaching) as well as by each relative day within the tooth bleaching and post-tooth bleaching period.

Days within the tooth-bleaching period will be relative to the Visit 2 [at home] result (day 1) up to and including the result recorded on the day prior to Visit 3. Days within the post-tooth bleaching period will be relative to the result following Visit 3 (at home) (day 1) and include any results up to and including the day of Visit 4. The daily mean ( $\pm$  SE) profiles of VAS, LMS and Bothersomeness scores across the study (clearly denoting each period) will be plotted by study product group.

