### Figure 3-1 Schematic of Flow of Key Study Assessments/Procedures

Subjects will then complete the whitening history questionnaire, the tooth sensitivity questionnaire and the DHEQ after being given instruction in the completion of these questionnaires. Subjects will be dispensed their at-home Tooth Sensitivity Questionnaires for completion daily. Subjects will then be dispensed the tooth bleaching kits for use at home. Subjects will be instructed in the correct use of the tooth bleaching product, the first application of which will be undertaken at the study site under supervision followed by supervised toothbrushing with their allocated dentifrice. Subjects will be scheduled to return to the study site for Visit 3 ( $7 \pm 1$  days) and will continue to use their assigned dentifrice twice daily and their tooth bleaching kit once daily per instructions and complete their Tooth Sensitivity Questionnaire at home, daily in the evening (including the evening of Visit 2).

At Visit 3, subjects will undergo a review of their current medications, and product compliance, return completed questionnaires and will then undergo an OST examination. The shade (color) of the facial surfaces of the anterior 6 maxillary and mandibular teeth (tooth numbers 6-11 and 22-27) will then be assessed in the same way as at Visit 1. Subjects will then complete the post whitening questionnaire and the DEHQ. Subjects will be scheduled to return to the study site for Visit 4 (2 weeks $\pm$ 2 days after the completion of peroxide tooth bleaching) and will continue to use their assigned dentifrice twice daily and complete their Tooth Sensitivity Questionnaire daily in the evening.

At Visit 4, subjects will undergo a review of their current medications and product compliance and return their completed Tooth Sensitivity Questionnaire and study products. Subjects will then undergo OST and OHT examinations and complete the DEHQ. Subjects will then exit the study.

Safety and oral tolerability of the study products will be monitored by review of reported AEs and medical device incidents collected at every study visit. Subjects of child-bearing potential shall confirm their pregnancy status at every site visit.

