## 5.1 Schedule of Activities

Table 5-1 Schedule of Activities

Procedure/Assessment	Screening	Study Period			
	Visit 1 (Day 1)	Visit 2 [start of tooth bleaching] (Day 15)	Visit 3 [completion of tooth bleaching] (Day 22)	Visit 4 [2 weeks post completion of tooth bleaching] (Day 36)	
Informed consent	X				
Medical history	X				
Demographics	X				
Current/prior/concomitant medication review	X	X	X	X	
Review of product compliance		X	X	X	
Return of completed Tooth Sensitivity Questionnaires			X	X	
Return study products				X	
OST Examination	X	X	X	X	
OHT Examination	X				X
Assessment of tooth color 	X	X	X		
DH assessments (EAR, MGI, tooth mobility and evaporative air sensitivity) 	X				
Review of inclusion/exclusion criteria	X				
Subject eligibility	X				
Subject completed the Whitening History questionnaire at site		X			
Subject completes tooth sensitivity questionnaire at site	X	X			
Subject completes the Post- Whitening questionnaire at site			X		
Subject completes the DHEQ at site 	X	X	X	X	
Stratification and Randomization to treatments 	X				
Dispense study products	X				
Supervised toothbrushing	X				
Subject dispensed tooth sensitivity questionnaire for at home completion 		X			
Subject dispensed tooth bleaching kit for at home use with first application followed by tooth brushing at study site under supervision 		X			
Adverse events review 	X	X	X	X	
Medical device incidents review 	X	X	X	X	
Study conclusion					X

Property of Haleon- Confidential

May not be used, divulged, published or otherwise disclosed without the consent of Haleon

Abbreviations: OST: Oral Soft Tissue, OHT: Oral Hard Tissue, DH: Dentine Hypersensitivity

Footnotes:

1. Adverse Events (AEs), Serious Adverse Events (SAEs) collected immediately after subject provides consent to participate in the study by the completion of the Informed Consent Form (ICF). Medical device in this study is the supplied toothbrush and medical device incidents will be recorded from first use of a medical device.
2. Tooth color assessed on the facial surfaces of the anterior 6 maxillary and mandibular teeth (tooth numbers 6-11 and 22-27) using the VITA Bleachedguide 3D Master.

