### 8.3.2 Secondary Endpoint Analyses

The VAS score for tooth sensitivity for the first 7 days during the tooth bleaching period will be analyzed using a Mixed Model with Repeated Measures (MMRM), with study product, DH diagnosis at screening (yes/no), days of bleaching and study product by days of bleaching interaction as fixed effects. The VAS score at screening will also be included as a covariate. Subject will be included as a repeated measure with compound symmetry covariance structure. Kenward Rogers degrees of freedom approach will be applied ([Kenward and Roger, 1997](#)). The overall (across all days) least square means (with SE and 95% confidence intervals [CI]) for each study product will be presented along with the difference (with SE and 95% CI).

A separate MMRM will be applied to evaluate the pairwise differences between products for each day. This will be identical to the above MMRM but subject will be included as a repeated measure with unstructured covariance matrix. In case of convergence issues, the Toeplitz, Autoregressive (1), Compound Symmetry covariance structures will be applied until convergence is attained (all heterogeneous versions first and then the same sequence of homogeneous versions). The least square means (with SE and 95% CI) for each study product will be presented along with the pairwise differences (with SE and 95% CI) between products for each day using the appropriate contrasts from the MMRM results.

As a further sensitivity analysis, the mean VAS score for tooth sensitivity over the tooth-bleaching period (Visit 2 [at home] to Visit 3) for a subject will be analyzed using an Analysis of Covariance (ANCOVA) model will be used with study product and DH diagnosis at screening (yes/no) as fixed effects and the VAS score at screening as a covariate. The least square means (with SE and 95% CI) for each study product will be presented along with the difference (with SE and 95% CI).

The LMS and the Bothersomeness scores during the tooth-bleaching period will be analyzed and presented in identical fashion to the VAS scores endpoint using the same MMRMs and ANCOVA (replacing the respective screening result as a covariate).

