## 9.13 Post-Whitening Questionnaire.

To be completed at Visit 3 after the completion of the peroxide tooth whitening.

Please tick the boxes that best answers the statements:

	Strongly Agree	Agree	Agree a Little	Neither Agree nor Disagree	Disagree a Little	Disagree	Strongly Disagree
	(7)	(6)	(5)	(4)	(3)	(2)	(1)
1) I am satisfied with the results of my tooth whitening.							
2) I found it inconvenient to switch my toothpaste for this study.							
3) I found my teeth to be painful during the tooth whitening treatment.							
4) I would recommend tooth whitening to a friend or relative.							
5) I would consider further tooth whitening treatments in the future.							
6) I had to change the way I ate or drank certain things during the tooth whitening treatment.							
7) Having sensations in my teeth during tooth whitening took pleasure out of eating and drinking .							
8) Having sensations in my teeth during tooth whitening was worrying to me.							

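### The bleaching period ends at Visit 3, which may fall 6, 7 or 8 days after Visit 2, so off schedule one diary day can sit in the wrong period and the models use different days

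*Combined protocol and SAP*

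**What the plan says.** **Treatment and visits**
- Section 7.1.1: "Subjects should perform peroxide bleaching for 7 consecutive days". The first application is supervised at the site, at Visit 2.
- Section 3, in the text with Figure 3-1: "Subjects will be scheduled to return to the study site for Visit 3" at 7 ± 1 days. Visit 4 is timed from the completion of bleaching, not from Visit 3.
- Table 5-1 heads the two columns "Visit 2 [start of tooth bleaching] (Day 15" and "Visit 3 [completion of tooth bleaching] (Day 22" (each column head ends with a closing bracket). Its footnote 4 describes one use at the site and then daily home use, with a total of 7 days in brackets.
- Section 9.13 heads the post-whitening questionnaire "To be completed at Visit 3 after the completion of the peroxide tooth whitening".

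**Analysis**
- Section 8.3.1: bleaching day 1 is the Visit 2 home diary, and the period runs "up to and including the result recorded on the day prior to Visit 3". The home diary after Visit 3 is post-bleaching day 1.
- Section 8.3.2: the MMRM uses the first seven days of the bleaching period. The ANCOVA, offered as a sensitivity analysis, uses the subject's mean "over the tooth-bleaching period (Visit 2 [at home] to Visit 3", with no seven-day limit. The negative binomial models count event days with an offset for completed days in the period, also without a limit. All of these are then repeated for the post-bleaching period, and the MMRM day range is not restated.
- Table 2-1 labels the endpoints by visit interval (2-3 and 3-4).

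**The concern.** The boundary between the two periods follows the visit date, while the exposure that defines the periods follows a seven-day course. The two agree only when Visit 3 falls exactly seven days after Visit 2. One day either side is allowed, and the plan does not say how the diary days of such subjects are to be labelled.

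The primary output is the daily profile by product during and after bleaching. Section 3 expects sensitivity to rise during bleaching and for 1 to 10 days afterwards. The days around the boundary are where a one-day shift in labels could show most. In addition, the ANCOVA is meant to support the MMRM, and it does so less clearly if it averages over other days.

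**Working it through.** **Inputs.** Diary day 1 = evening of Visit 2. Seven consecutive applications (Section 7.1.1), so the last is on diary day 7 if none is missed or late. Visit 3 at Visit 2 + 6, + 7 or + 8 days (Section 3). Period rule from Section 8.3.1; MMRM and ANCOVA day sets from Section 8.3.2.

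**Nominal schedule.** 22 − 15 = 7. The bleaching period is then diary days 1 to 7, which matches the seven applications. No day is misplaced.

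**Day count at each allowed timing**

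| Visit 3 | Period under 8.3.1 | MMRM days | ANCOVA days | Day affected |
|---|---|---|---|---|
| +6 | days 1–6 | 6 | 6 | day 7 labelled post-bleaching day 1 |
| +7 | days 1–7 | 7 | 7 | none |
| +8 | days 1–8 | 7 | 8 | day 8, no planned application, counted as bleaching |

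At +6, the day-7 diary is collected but is lost from the bleaching-period MMRM. It covers a bleaching day only if the seventh application is still taken, and no section says whether it is. It would be about 1/14 = 7.1% of that subject's post-bleaching mean. At +8, day 8 is 1/8 = 12.5% of that subject's ANCOVA mean, and post-bleaching day 1 is two days after the last application.

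**Other readings of the text**
- If the ANCOVA interval in Section 8.3.2 includes the day of Visit 3, it uses 7, 8 or 9 days against 6, 7 or 7 in the MMRM, so the sets differ at every timing.
- If the seven-day limit carries over literally to the post-bleaching period, the MMRM uses 7 days and the ANCOVA about 14 (15 with the day of Visit 4).
- If Table 5-1 footnote 4 means one site use plus seven home uses on separate days, the last application is on diary day 8. That is the nominal day of Visit 3, so it would be labelled post-bleaching even on schedule.

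**Effect on the profile (illustration).** The documents give no decay rate and no distribution of visit days, so both are assumed. Let mean VAS be 20 mm on bleaching days, multiplied by d on each day after. Let a share w of subjects be seen at +6 and the same share at +8, with the seventh application taken. The diary labelled post-bleaching day 1 then averages 20 × [w + (1 − 2w)d + w·d²]. The aligned value is 20d.

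| w | d | Labelled day 1 | Aligned | Shift |
|---|---|---|---|---|
| 1/3 | 0.50 | (20 + 10 + 5)/3 = 11.67 mm | 10.0 mm | +16.7% |
| 1/3 | 0.75 | (20 + 15 + 11.25)/3 = 15.42 mm | 15.0 mm | +2.8% |
| 1/3 | 0.90 | (20 + 18 + 16.2)/3 = 18.07 mm | 18.0 mm | +0.4% |
| 0.15 | 0.50 | 3 + 7 + 0.75 = 10.75 mm | 10.0 mm | +7.5% |

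If subjects at +6 do not take a seventh application, their label is correct and the shift changes sign. For w = 1/3 and d = 0.50 it is (10 + 10 + 5)/3 = 8.33 mm, or −16.7%.

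**Effect on the ANCOVA difference.** Let f be the share of subjects at +8 and r the day-8 product difference relative to a bleaching day. Dilution is f(1 − r)/8. For f = 0.10, r = 0 it is 1.25%; for f = 1/3, r = 0.5 it is 2.1%; for f = 1/3, r = 0 it is 4.2%. The ceiling (f = 1, r = 0) is 12.5%.

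**With a fixed day set.** Taking bleaching as diary days 1 to 7 and post-bleaching day 1 as day 8 gives seven bleaching days at +6, +7 and +8. No day is misplaced, and the MMRM and ANCOVA use the same days, for subjects who take all seven applications on time.

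**The case against.** A one-day window around a matching nominal visit is ordinary tolerance, and Table 2-1 defines the endpoints by visit interval on purpose. The seven-day limit already keeps day 8 out of the main secondary model, so under Section 8.3.1 the two day sets differ only for subjects at +8. The ANCOVA is a sensitivity analysis, the primary analysis is descriptive, and the study has no formal success criterion. The diary looks back 24 hours and the time of bleaching is not fixed, so no boundary is exact to the day. Section 8.3.6.2 already summarizes bleaching occurrences and missed or additional ones, and Section 8.3 allows clarification before unblinding. All of this stands and keeps the point minor. None of it says how a subject at +6 or +8 is to be labelled, or which days the post-bleaching MMRM uses.

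A reader might go further and infer that the plan routinely swaps bleaching and post-bleaching days, or that it biases the product comparison. The documents do not support either. The nominal schedule misplaces nothing under the seven-application reading, and nothing links visit timing to arm. In the illustration, if the arms' profiles are proportional, their difference on day 1 shifts by the same percentage as the mean, so attenuation does not follow.

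A reader might also conclude that the boundary belongs at each subject's last application. That date is a post-randomisation outcome. A subject who stops on day 3 because of pain would have days 4 to 7 relabelled post-bleaching. If stopping depends on the dentifrice, so does the length of the period. The visit-based cut does not have this weakness, and its replacement should not introduce it.

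**Conclusion.** The point holds as a minor one. The visit-based cut is right on schedule. At +8 it places one day without a planned application in the bleaching period for every analysis except the MMRM. At +6 it removes the day-7 diary from the bleaching-period MMRM and, if the seventh application is taken, labels a bleaching day as post-bleaching. The limit of one diary day per subject assumes seven applications with none missed or late.

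The main consequence is some blurring of the early post-bleaching profile. The range of about +0.4% to +17% on post-bleaching day 1 rests on one third of subjects at each timing, daily declines of 10% to 50%, and a seventh application taken at +6. The upper end needs both the even spread and daily halving, neither of which the documents give, so it should not be quoted as the expected size. For shares of 10% to one third at +8 with no product difference left on day 8, the ANCOVA difference is diluted by 1.25% to 4.2%. No directional bias between arms is shown.

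The unstated post-bleaching MMRM range concerns every subject, and it needs a decision before programming.

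**What to change.** 1. In Section 8.3.1, define the bleaching period as diary days 1 to 7 counted from the Visit 2 evening, and post-bleaching day 1 as diary day 8, whatever the date of Visit 3.
2. In Section 8.3.2, use this day set in the MMRM, the ANCOVA and the negative binomial models. State one post-bleaching day range for all of them.
3. Align the visit-interval labels in Table 2-1.
4. Use the date of the last application only in a supportive analysis.
5. Reconcile the Visit 3 window, the number of applications (Section 7.1.1 and Table 5-1 footnote 4) and the description of Visit 3 as the completion of bleaching (Table 5-1 and Section 9.13). A subject seen at +6 may have the shade score and questionnaire before a seventh application. The range in item 1 follows the seven consecutive days of Section 7.1.1 and must match the reconciled text.

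The cost is small wording and programming changes, using diaries already collected, with no extra subjects or visits. The drawback is that subjects who stop bleaching early stay in the bleaching period to day 7. In exchange, period length does not depend on treatment.
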